- Use with caution in patients with cerebral or coronary insufficiency, Raynaud's phenomenon, thromboangiitis obliterans, scleroderma, or Sjögren's syndrome.
- Advise patients to seek immediate medical care if signs and symptoms of acute narrow-angle glaucoma develop.

The most common adverse reactions (incidence > 1%) are application site dermatitis, worsening inflammatory lesions of rosacea, application site pruritus, application site erythema, and application site pain. In clinical trials, adverse reactions occurred in 1% - 2% of subjects treated with RHOFAD[™] through 4 weeks of treatment. In the long-term (open-label) clinical trial, the rates of adverse reactions over a one-year treatment period were as follows: worsening inflammatory lesions of rosacea (3%), application site dermatitis (3%), application site pruritus (2%), application site pain (2%), and application site erythema (2%). Subjects with persistent erythema along with inflammatory lesions were allowed to use additional therapy for the inflammatory lesions of rosacea [8].

STUDY DESIGN

This is a prospective, two-arm randomized, baseline-controlled, pilot study to evaluate the efficacy of combined Vbeam PDL and topical RHOFAD[™] cream for improvement in erythematotelangiectatic rosacea.

[figure not shown]
Up to 60 healthy male or female subjects will be enrolled at two investigational sites. All subjects will undergo an assessment of their general health. Following enrollment, subjects will be randomized to a study arm. Subjects in Arm 1 will receive RHOFADÉ topical cream at the screening visit and will be instructed to apply it daily for 4 weeks prior to the first PDL facial treatment. Arm 1 subjects will receive three (3) monthly PDL facial treatments at 4-week intervals. Subjects will apply RHOFADÉ topical cream once daily during the 6-month study, according to the study protocol, with a 3-day wash-out period prior to each PDL treatment. Immediately following the PDL treatment, subjects in Arm 1 will apply RHOFADÉ topical cream in-office. If subjects find it irritating to the skin to apply RHOFADÉ immediately after PDL treatment, then they may apply it within 24 hours of subsequent treatments.

Arm 2 subjects will receive RHOFADÉ topical cream at the screening visit and will be instructed to apply it daily for 6 months of continuous use until the 6-month post-baseline follow-up visit. . Subjects in Arm 2 will not receive laser therapy.

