Comfort assessment will be performed independently by the subject using a numerical scale response (NSR) scale 0=No pain to 10=Worst possible pain (*Appendix III*). Subjects will be asked to fill out a questionnaire after each PDL treatment (Tx.1 – Tx.3).

Primary Efficacy Endpoint:

- Clinician erythema assessment (CEA): 5-point scale (0=Clear to 4=Severe) at 6-month follow-up compared to baseline.
- Subject self-assessment (SSA) 5-point scale similar to CEA at 6-month follow-up compared to baseline.

Secondary Efficacy Endpoints:

- Investigator and subject assessment of overall changes in skin condition (skin texture, vessel size, flushing), using a Global Aesthetic Improvement (GAI) 5-point scale (0=Excellent improvement to 4=No difference) – *Appendix IV, Table 4.*
- Investigator assessment of improvement in vessel size – *Appendix IV, Table 5.*
- Subject satisfaction 5-point scale (0=Very satisfied to 4=Very dissatisfied) – *Appendix IV, Table 6.*

Safety Endpoints:

- The number, severity and type of any adverse event recorded throughout the study and post-treatment (discomfort (pain), immediate and delayed response).
- Occurrence of expected post-treatment immediate response following each treatment based on a predefined scale (*Appendix IV, Table 3*).
- Discomfort (pain) level using a 10-point visual analog scale will also be recorded after each PDL treatment, using a Numerical Scale Response (NSR) – *Appendix III.*

Study Duration

The duration of the entire study from first subject enrollment to last subject completing the 6-month follow-up, is expected to be approximately 1 year.

Subject Population

Up to 60 healthy male and female adults (greater than 18 years of age), who meet the inclusion and exclusion criteria.

Subjects enrolled in the study can discontinue their participation at any time, for any reason, without prejudice or reduction in the quality of their medical care. In addition, the investigator or the sponsor can terminate a subject's participation in this study to protect the subject's health or if the subject is not compliant with the study protocol and schedule. Subjects may be replaced if withdrawn or lost from the study.

All subjects enrolled into this study must meet the following criteria:

Inclusion Criteria:

1. Subject is a healthy male or female of 18 to 75 years of age.

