9. Subject has an infection or is suffering from current or has a history of significant skin conditions in the treated area or inflammatory skin conditions, including, but not limited to: photodermatoses, active acne, excessive skin dryness, psoriasis, eczema, rash, open wounds, varicella scars, open lacerations or abrasions and active cold sores or herpes sores prior to treatment (duration of resolution as per the Investigator’s discretion) or during the treatment course.

10. Having a known anticoagulative or thromboembolic condition or taking anticoagulation medications one week prior to and during the treatment course (to allow inclusion, temporary cessation of use might be requested as per the subject's physician discretion).
11. Use of non-steroidal anti-inflammatory drugs (NSAIDS, e.g., ibuprofen-containing agents) one week before and after each treatment session.
12. Subject has a history of pigmentary disorders, particularly tendency for hyper- or hypo-pigmentation.
13. Subject has a history of keloid scarring or of abnormal wound healing.
14. Subject has a known photosensitivity to the device's laser wavelengths, history of ingesting medications known to induce photosensitivity, or history of seizure disorders due to light.
15. Subject has undergone any surgical, light-based therapy or RF procedures in the treatment area within 3 months of treatment or during the study.
16. Having undergone any other surgery in the treated area within 3 months of treatment (or more if skin has not healed completely) or during the study.
17. Subject has a tattoo or permanent make-up in the treated area.
18. Subject has systemically used retinoids or antioxidants within 1 month of treatment or during the study.
19. Excessively tanned in areas to be treated or unable/unlikely to refrain from tanning during the study.
20. Participation in a study of another device or drug within three months prior to enrollment or during the study.
21. As per the Investigator's discretion, any physical or mental condition which might make it unsafe for the subject to participate in this study.

Study Procedures

The following table provides a summary of the required study visits and the procedures and assessments performed at each visit.

Table 2: Study Schematics

Visit	Screening /Baseline	Tx 1* / 1-month FU	1-week (± 2 days) Safety Evaluation	Tx 2 - 3 / 2 & 3-Month FU Visits (4± 1 week)	6-Month (± 2 weeks) FU
Informed Consent	X				
Medical History	X				

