- Once the consent form is signed, the subject will be assigned the next consecutive subject number and will be randomized to a treatment arm.
- Women capable of childbearing will undergo a urine pregnancy test.

- Skin type will be recorded using the Fitzpatrick Scale.
- Test spots may be performed (optional) for subjects in Arm 1 to determine the subject's response to selected treatment parameters. Test spot locations will be selected by the investigator.
- Subjects in Arms 1 & 2 will be provided with RHOFADE topical cream and instructed to apply once daily, according to the drug insert instructions: apply a pea-sized amount once daily in a thin layer to cover the entire face (forehead, nose, each cheek, and chin) avoiding the eyes and lips.
- The RHOFADE topical cream will be applied daily for 4 weeks prior to the first PDL facial treatment.
- Subjects must discontinue topical use for a 3-day washout period prior to each PDL treatment.

Pre-Treatment PDL Care

In order to minimize pain during laser irradiation, subjects will be offered to use topical anesthetic cream (EMLA), which will be applied to the skin surface 30-60 minutes prior to laser irradiation.

PDL Treatment Procedure

- Treatments will be performed every 4 (± 1) weeks. Subjects in Arm 1 must discontinue topical use for a 3-day washout period prior to each PDL treatment.
- Laser treatment procedures will conform to all laser safety instructions and should be conducted per the procedure described.
- The investigator, all personnel in the treatment room and the subject will wear protective eyewear, appropriately rated for the device wavelength(s) being operated.
- Based on the subject's response to the test spot evaluation (optional) or experience from treatment of prior subjects in this study or in practice, the investigator will select the parameters used for treatment, based on the threshold for nonpurpuragenic settings.
- Parameters include choice of: the 12 mm or 15 mm spot size, the laser fluence, the duration of the laser pulse exposures and the cooling procedure. The investigator will treat the face with the parameters chosen and will document the parameters.
- The treatment area will be photographed before each treatment and at each post-treatment follow-up visit. Optional photography can include photos at 10 minutes (approximately) after each treatment.
- All subjects will be treated as follows:
 - The 12 mm or 15 mm spot size will be used.

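### Randomised subjects who leave may be replaced and nothing keeps them in the analysis, so the 6-month comparison of arms could become one of retained subjects plus substitutes

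*Combined protocol and SAP*

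**What the plan says.** Under Screening Procedures, once consent is signed "the subject will be assigned the next consecutive subject number and will be randomized to a treatment arm". Study Design likewise places randomisation right after enrolment and sets the size: "Up to 60 healthy male or female subjects will be enrolled at two investigational sites". It gives no allocation ratio and does not say whether replacements count within the 60.

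Under Subject Population there are three routes out after randomisation:

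- The subject's own choice: "Subjects enrolled in the study can discontinue their participation at any time, for any reason".
- Removal by the investigator or the sponsor to protect the subject's health.
- Removal by either of them "if the subject is not compliant with the study protocol and schedule".

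The paragraph then ends: "Subjects may be replaced if withdrawn or lost from the study". No limit is set by number, arm, timing or reason.

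The primary objective (Study Synopsis and Study Design) has two parts: Arm 1 at 6 months against its own baseline, and Arm 1 against Arm 2 at 6 months. The primary endpoints, CEA and SSA, compare the 6-month score with baseline.

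Data Analysis names no analysis population and no rule for missing scores. Its efficacy text mentions only the comparison with baseline. The Study Termination Procedure ties the termination visit to the last follow-up visit, and Table 2 places it at 6 months. No assessment at early exit, and no later follow-up of those who leave, is described.

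**The concern.** Randomisation makes the arms comparable at the start. Staying for six months is decided afterwards, and it can depend on the arm and on how well the subject is doing. If leavers fall out of the 6-month comparison and newcomers fill the numbers, the comparison is no longer between the groups that were randomised.

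Loss could plausibly differ between arms here. No sham laser or masking is described, so Arm 2 subjects know that they get no laser. Only Arm 1 has laser sessions, treatment pain and repeated washouts. The investigator, who may end a subject's participation, also scores global improvement and vessel size, so removal for non-compliance could be decided with arm and response both known.

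At stake is the between-arm half of the primary objective. The comparison with baseline within Arm 1 would also be affected if poorer responders leave that arm.

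**Working it through.** The plan has no figure to reproduce. The limit of 60 has no alpha, power, effect size, SD or dropout rate behind it. What follows shows the possible size under stated assumptions.

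**1. Do the provisions combine as feared?** Randomisation comes at screening, so nearly every loss is after randomisation. The primary endpoint needs a 6-month score. Those who leave have no planned 6-month score. No sentence keeps them in the analysis, and none removes them. If the plan is followed as written, the 6-month data come mainly from retained subjects plus anyone enrolled later.

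**2. Shift from omitting leavers.** Assumptions, none of them from the documents:
- change scores are roughly normal, with SD 0.8 to 1.0 grade;
- 30 subjects per arm (60 divided equally);
- a fraction d is lost from one arm only, all from its less-improved half, so the chance of leaving is 2d below the median and 0 above it.

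Each half of a normal distribution has its mean 0.798 × SD from the centre. Among those who remain, the better half has weight 0.5 and the worse half 0.5(1 − 2d), out of a total of 1 − d. Hence

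shift = 0.798 × SD × [0.5 − 0.5(1 − 2d)] / (1 − d) = 0.798 × SD × d / (1 − d)

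SE of the arm difference = SD × √(2/30)

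| Loss d | Shift, SD 0.8 | Shift, SD 1.0 | Shift ÷ SE |
|---|---|---|---|
| 10% | 0.07 | 0.09 | 0.34 |
| 20% | 0.16 | 0.20 | 0.77 |

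The SE is 0.21 (SD 0.8) to 0.26 (SD 1.0). The last column does not depend on the SD.

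**3. Direction.** The arm that loses its less-improved subjects looks better than it is. If that is Arm 2, the benefit of the combination is understated; if it is Arm 1, overstated. Nothing in the documents says which is more likely.

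**4. What replacement adds.** The shift formula has no term for replacement: the bias is the same whether or not the gaps are filled, if substitutes are subject to the same selection. Replacement changes the apparent precision. At 20% loss, 24 remain in the affected arm. Without replacement the SE is SD × √(1/30 + 1/24) = 0.274 SD. With replacement to 30 it is SD × √(2/30) = 0.258 SD, about 6% smaller around the same biased estimate.

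A simulation shows the same pattern. It used a two-sided 5% t-test with no true difference, SD 1, one-arm loss moderately related to outcome (logit slope 1 per SD) and 4,000 runs per case.

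| Loss | Mean shift (SD) | False positives, completers only | With replacement to 30 |
|---|---|---|---|
| 10% | 0.09 | 6.3% | 6.6% |
| 20% | 0.18 | 9.8% | 10.5% |
| 30% | 0.25 | 13.4% | 16.5% |

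Most of the excess over 5% is already there without replacement. At 10% and 20% loss the further increase is about the size of the simulation error.

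**5. Numbers if nobody is substituted.** Of 60 randomised, 60 × (1 − d) have 6-month data: 54 at 10% loss and 48 at 20%. Reaching 60 with 6-month data needs 60 / (1 − d): 67 or 75 randomised.

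**The case against.** The strongest reply is that the text says subjects may be replaced, not that they leave the analysis. That is correct. A reader might infer that replaced subjects are excluded, or that replacement can serve no other end. The documents support neither: topping up enrolment to keep enough 6-month observations is compatible with analysing everyone. Exclusion is only what the silence on the analysis set and on follow-up makes likely.

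A reader might also infer that a substitute takes over the vacated place in the same arm. Screening Procedures points the other way: each newly consented subject gets the next number and is randomised, and no section exempts replacements. Saying so explicitly is a clarification.

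A third tempting reading is that Exclusion Criteria item 11, which bars NSAID use "one week before and after each treatment session", will make Arm 1 lose subjects through removal. This is weak support. It is listed as an entry criterion, no section says that a breach leads to removal, and removal is discretionary. Several other continuing restrictions, such as those on tanning and on other procedures, apply to both arms.

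Finally, this is a pilot with no stated test or error rate, and loss unrelated to outcome would cause no bias. That lowers the stakes. It does not remove the point, because the comparison of arms is in the primary objective and nothing written protects it.

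**Conclusion.** The concern holds as a risk that the plan leaves open. The primary comparison of Arm 1 with Arm 2 could become one of retained subjects plus substitutes, because leavers may be replaced and nothing keeps them in the analysis or collects their 6-month scores. The main source of bias would be the omission of leavers. Replacement fails to repair it and adds a little false precision, so a reader should not conclude that the replacement rule by itself creates the bias.

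The size cannot be derived from the documents. In the illustration, 20% one-sided loss moves the arm difference by about 0.8 of its standard error, and 10% by about a third. These figures rest on the assumed SD, equal arms and loss confined to the less-improved half of one arm. Loss of a similar kind in both arms would partly cancel. The plan should be changed on this point, though a pilot is not invalidated by it.

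**What to change.** In Subject Population, replace the replacement sentence with text to this effect:

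> Additional subjects may be enrolled, but they do not substitute for subjects who have left. Each receives the next randomisation assignment, as under Screening Procedures. Every randomised subject stays in the efficacy analysis in the assigned arm. Subjects who stop study treatment or do not comply are asked to attend the remaining scheduled CEA and SSA assessments, including 6 months, where they agree. Withdrawals are reported by arm and reason.

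State also whether additional subjects count within the 60.

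In Data Analysis, say that missing 6-month scores are handled by an analysis that uses all collected visits (for example a repeated-measures model with arm, visit and their interaction), with a sensitivity analysis in which the missing scores are assumed worse than predicted. Earlier scores should not be carried forward. In Arm 1 the 1-month score is taken before the first laser treatment, so carrying it to 6 months would count a cream-only result as a result of the combination.

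The grounds on which treatment or participation may be ended are left as they are.

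The cost is a few sentences in the protocol, some visits for subjects who are off treatment, and somewhat fewer complete 6-month scores per subject randomised: 54 or 48 of 60 at an assumed 10% or 20% loss. Continued attendance by leavers would reduce that loss.

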Early diagnosis and treatment based on subtype are recommended to halt progression of symptom severity [5]. Flushing is better prevented rather than treated, by avoiding specific triggers, decreasing transepidermal water loss by moisturizers, and blocking ultraviolet light [5]. Nonselective β -blockers and α 2-adrenergic agonists decrease erythema and flushing [5], while pulsed dye laser [5, 6] and intense pulsed light are used for telangiectasias [5]. Pulsed dye laser also addresses the diffuse erythema and enlarged pores characteristic of rosacea [6].

Oxymetazoline hydrochloride 1% cream (RHOFADE[™]) is a newly FDA-approved topical medication for adult rosacea patients. A primarily alpha-1a agonist, oxymetazoline hydrochloride (HCl) is thought to diminish erythema through vasoconstriction [7]. RHOFADE was evaluated for the treatment of persistent erythema associated with rosacea in two identical, randomized, double-blind, vehicle-controlled, parallel-group clinical trials [8]. A total of 489 subjects with persistent facial erythema associated with rosacea were treated with RHOFADE once daily for 4 weeks. An additional 440 subjects with persistent facial erythema associated with rosacea were also treated with RHOFADE once daily for up to one year in a long-term (open-label) clinical trial [8]. Disease severity was graded by the clinician using a 5-point clinician erythema assessment (CEA) scale [4] and by the subject on a similar 5-point subject self-assessment (SSA) scale, on which subjects scored either “moderate” or “severe” on both scales. Composite success, defined as the proportion of subjects achieving at least a 2-grade improvement on both CEA and SSA, was 15% in Trial 1 and 12% in Trial 2 on Day 29 of treatment [8].

Nonpurpuragenic pulsed dye laser (PDL) and intense pulsed light treatment have resulted in significant reduction in cutaneous erythema, telangiectasia and patient-reported associated symptoms of erythematotelangiectatic rosacea [9]. The PDL is an ideal energy-based device to treat the cutaneous vasculature of rosacea, since the 595nm wavelength is strongly taken up by the hemoglobin in blood vessels [6, 10]. With Vbeam 595nm PDL, ultra-long pulse durations reduce purpura while treating the telangiectasias associated with rosacea, which is more comfortable for patients [5, 6].

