2. Subject has erythematotelangiectatic rosacea with clinician erythema assessment (CEA) and subject self-assessment (SSA) of “moderate” or “severe” (Grade 3 or 4).
3. Fitzpatrick Skin Type I – VI.
4. Subject must be able to read, understand and sign the Informed Consent Form.
5. Subject must be willing and able to adhere to the treatment and follow-up schedule and post-treatment care instructions.
6. Subject must be willing to have limited sun exposure for the duration of the study, including the follow-up period up to 6 months post-baseline.
7. Subject is willing to have photographs taken of the treated area that will be used, de-identified, in evaluations and may be used, de-identified, in presentations and/or publications.
8. For female candidates – subject must be post-menopausal, or surgically sterilized, or using a medically acceptable form of birth control during the entire course of the study.

Exclusion Criteria:

1. Subject is pregnant or planning to become pregnant during the study duration.
2. Subject has an active electrical implant anywhere in the body, such as a pacemaker or an internal defibrillator.
3. Subject has an implant in the treated area (such as metal plates or screws) or an injected chemical substance.
4. Subject has a known collagen (connective tissue) disorder, vascular disease, scleroderma or other autoimmune disease (i.e. rheumatoid arthritis, lupus).
5. Subject has a history of diseases stimulated by heat or sun exposure, such as recurrent Herpes Simplex in the treated area, unless treatment is conducted following a prophylactic regimen.
6. Subject has a history of immunosuppression/immune deficiency disorders (including HIV infection or AIDS) or currently using immunosuppressive medications.
7. Having or undergoing any form of treatment for active cancer or having a history of skin cancer or any other cancer in the areas to be treated, including presence of malignant or pre-malignant pigmented lesions.
8. Subject is suffering from significant concurrent illness, such as cardiac disorders, diabetes (type I or II), or pertinent neurological disorders.

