After treatment, no special care is usually necessary for the treatment site. Aquaphor (similar to Vaseline) may be supplied to the subject to be applied to any area that feels irritated. The subject will also be instructed to apply cool compresses if they have any areas of swelling after treatment and to wash the treated area with soap or a gentle cleanser as they normally would for the week following treatment. The subject will be able to continue with their preferred routine skin care, excluding any method of wrinkle removal, the day after treatment. Sunscreen should be worn.

Data Recording

All data will be recorded in source documents and transcribed onto Case Report Forms (CRFs). Site will be monitored by Syneron staff or designees to assure adherence to the clinical trial requirements, subject safety, protocol procedures, and for data accuracy. The Case Report Forms and images will be reviewed and retrieved during the monitoring visit. All source documentation will remain in the subject's files at the site.

Protocol Revisions and/or Deviations

With the exception of emergency situations, no changes or deviations in the conduct of this protocol will be permitted without the prior approval of the sponsor.

The IRB/IEC that granted original approval for the study must be notified of all changes in the protocol and will approve any change or deviation that may increase risk to the subject, and/or that may adversely affect the rights of the subject or validity of the investigation.

 Candela Corporation Confidential	Pilot Study to Evaluate Combined Vbeam[®] Pulsed Dye Laser Treatment and RHOFADE[™] (oxymetazoline hydrochloride) Topical Cream for Erythematotelangiectatic Rosacea			
	Protocol #	DHF24671	Rev. Date	June 11, 2018

In the event of an emergency, the Investigator will institute any medical procedures deemed appropriate. However, all such procedures must be promptly reported to the sponsor and the IRB/IEC.

ADVERSE EVENTS (AE)

An adverse event (AE) is any adverse change in health or side effect that occurs in a study participant during their participation in the study.

Anticipated Adverse Effects

Anticipated adverse effects of laser-based treatments include: hyperpigmentation, blistering, crusting, bruising, scabbing, scarring, hypopigmentation, infection, and pinpoint bleeding. While unlikely, some adverse events may be permanent.

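### No eligibility item covers recent or current RHOFADE or other topical erythema-lowering therapy before baseline, and later changes in such therapy are not systematically recorded

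*Combined protocol and SAP*

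**What the plan says.** Inclusion Criterion 2 sets the erythema entry rule: "Subject has erythematotelangiectatic rosacea with clinician erythema assessment (CEA) and subject self-assessment (SSA) of" moderate or severe, Grade 3 or 4. It attaches no condition about rosacea medicines in use when the score is taken.

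The primary endpoints build on that score: "Clinician erythema assessment (CEA): 5-point scale (0=Clear to 4=Severe) at 6-month follow-up compared to baseline" and "Subject self-assessment (SSA) 5-point scale similar to CEA at 6-month follow-up compared to baseline". The primary objective asks for two comparisons at 6 months: Arm 1 against its own baseline, and Arm 1 against Arm 2 (cream alone). The Efficacy paragraph under Data Analysis names only the comparison with baseline.

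The Background recognises that medicines move this outcome. It reports that nonselective beta-blockers and alpha "2-adrenergic agonists decrease erythema and flushing", and that oxymetazoline is thought to reduce erythema by vasoconstriction.

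Some exclusions do deal with medicines, for example "currently using immunosuppressive medications" (exclusion 6) and "Subject has systemically used retinoids or antioxidants within 1 month of treatment or during the study" (exclusion 18). None names RHOFADE or any topical rosacea product. Table 2 has a Medical History row at screening and a Change to Medical History row at each later visit, but no row for concomitant medication.

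**The concern.** The subjects are people seeking treatment for facial redness, and the study cream is an approved product. Someone who is using it at screening and still scores Grade 3 or 4 meets the criteria as written. Their on-cream score becomes the baseline, and they are then given the same cream as study treatment. For that subject the 6-month change cannot show the benefit of starting the cream. For a new user it can. The Arm 1 mean would mix the two kinds of change, with no means of separating them.

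A second route opens after randomisation. One arm receives laser and the other does not, subjects know which they are in, and no blinding of CEA or SSA is described. Outside redness therapy that is started, stopped or changed during the six months could differ between arms and move the 6-month scores. If use is not asked about at each visit, the analysis can neither detect nor describe it.

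**Working it through.** The plan gives no figure to reproduce here. The check reads the rules against each other and then works out which comparison is exposed.

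**Step 1. Does any rule reach topical erythema-lowering therapy?**
- Exclusions 15 and 16 cover surgical, light-based and RF procedures within 3 months. These are procedures, not medicines.
- Exclusions 6, 10 and 11 cover immunosuppressants, anticoagulants and NSAIDs, none of them as erythema treatment.
- Exclusion 14 covers ingested photosensitising medicines, and exclusion 18 covers systemic retinoids or antioxidants. Neither reaches topicals.
- Exclusions 4 (vascular disease) and 8 (cardiac disorders) may remove some beta-blocker users, by diagnosis and not by drug.
- Exclusion 20 reaches a drug only if it was taken in another study. Exclusion 21 is a safety-discretion clause.

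Systemic agents are therefore caught in part and by accident. RHOFADE and other topicals are not reached.

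**Step 2. Does a washout protect the baseline?** The only washout is of the study cream before each PDL session in Arm 1. It comes after baseline and does not touch what was used before it.

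**Step 3. Would later use be recorded?** Follow-up Study Visits calls for a brief review of medical-history changes at months 1, 2, 3 and 6 in both arms. A new medicine might be noted there, but nothing requires the question. Elsewhere, concurrent medications appear only in the adverse event text, for reactions that the investigator deems related to the device.

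**Step 4. Which comparison is affected?** Write improvement in grades as follows, assuming that effects add:
- c = effect of the cream in a subject starting from no therapy
- l = further effect of the laser
- p = share of subjects already on the cream at baseline
- a = effect of another erythema-lowering agent
- q1, q2 = shares of Arms 1 and 2 who start such an agent after randomisation

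A new user in Arm 1 changes by c + l. A current user changes by l, either because the cream's effect is already in the baseline or because the cream does not work for that subject.

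- Arm 1 mean change = (1 − p)(c + l) + p·l = l + (1 − p)c. The shortfall against an arm of new users is p·c.
- Arm 2 mean change = (1 − p)c.
- Between-arm difference with the same p in both arms = l. Prior use cancels.
- If the shares happen to be p1 and p2, the difference is l − (p1 − p2)c. Its expectation is still l, because prior use precedes randomisation.
- With an agent started after randomisation, the difference is l + (q1 − q2)a. Randomisation does not set q1 equal to q2, and the sign is open.
- Stopping an agent that was in use at baseline enters with the opposite sign.

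**Step 5. Can a number be attached?** The documents do not give p, q1, q2 or a. For c, the Background gives composite success (at least 2 grades on both scales) of 15% and 12% at Day 29 in two earlier trials. That is a responder rate at four weeks, not a mean grade change at 6 months, and this protocol defines no composite responder endpoint. The terms p·c and (q1 − q2)a therefore cannot be evaluated.

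**The case against.** The strongest reply is that both arms use the cream, so the randomised comparison isolates the laser, and prior use is balanced in expectation. That stands. A reader might infer that an on-cream baseline biases the between-arm result; Step 4 shows that it does not in expectation. The exposure from prior use is confined to the Arm 1 change from baseline. That change is nonetheless half of the primary objective and the only comparison named in the Efficacy paragraph.

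Other stronger readings are also tempting, and the documents do not support them:
- **That outside therapy goes unrecorded.** The Change to Medical History row is present at every post-baseline visit and may pick some of it up. What is missing is a requirement.
- **That subjects in both arms are permitted outside rosacea products.** Post-treatment Care says "The subject will be able to continue with their preferred routine skin care, excluding any method of wrinkle removal, the day after treatment". That refers to the day after laser, so it grants Arm 2 nothing, and routine skin care is not permission to use rosacea medicines.
- **That no systemic medicine is controlled.** Exclusions 4, 8, 14 and 18 catch some users, incidentally.
- **That Arm 2 will add more therapy and the difference will shrink.** This is possible, but nothing in the documents shows it, and extra use in Arm 1 would push the other way.
- **That the 12–15% success rates give a size.** For the reasons in Step 5, they do not.

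It is also fair to say that this is a pilot with no stated hypothesis test, and that a total ban on outside therapy would be a clinical decision. Both points limit the remedy but do not remove the gap.

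**Conclusion.** The point holds in a limited form. As written, the criteria admit a current user of the study cream at Grade 3 or 4, and that on-drug score then serves as the baseline for the Arm 1 primary change. The distortion equals the share of such users multiplied by the cream's effect, and it understates the change that new users would show. The between-arm comparison is protected in expectation against prior use, but not against therapy started or stopped after randomisation, which the plan does not systematically capture.

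The size is unknown: the documents give neither the frequency of outside use nor its effect on CEA or SSA. The conclusion rests on the full lists of inclusion and exclusion criteria, Table 2 and the visit procedures. The algebra assumes additive effects and serves only to show direction and which comparison is exposed. The documents do not show that such use occurs, only that the rules allow it at entry and do not require it to be recorded afterwards.

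**What to change.** 1. Add an eligibility item, anchored to the screening/baseline visit, on recent use of oxymetazoline and other erythema-lowering rosacea therapy. The sponsor should set the list of agents and the interval.
2. Add a concomitant-medication row to Table 2 at baseline and at every visit in both arms, covering rosacea and vasoactive medicines, with start, stop and change recorded.
3. In Data Analysis, commit to reporting such use by arm. Repeat the primary CEA and SSA comparison in a sensitivity analysis that accounts for subjects who started, stopped or changed such therapy, and state the handling in advance. It should stand beside the analysis of all randomised subjects, not replace it, because later use is itself a post-randomisation event.

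Whether such therapy is allowed during the study is for the sponsor to decide; the request is that the protocol states a position and that use is recorded.

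The cost is a short amendment and one extra CRF item. The downside is that some current users are delayed or not enrolled.
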